4. STUDY OBJECTIVE

The primary objective of this study is to determine the stability of the IOPCL-AMD-MAG to successfully adhere to a pseudophakic intraocular lens without rotation or slippage.

The secondary objective of this study is to determine if the IOPCL-AMD-MAG can improve uncorrected near visual acuity in subjects previously implanted with an Alcon SN60WF or SA60AT monofocal intraocular lens.

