4.1. Safety Endpoints

- Preservation of BCDVA Proportion of eyes (< 5%) that lose two or more lines of BCDVA (≥10 letters on the ETDRS chart) at 12 months from baseline.
- Preservation of BCNVA Proportion of eyes (<5%) that lose two or more lines of BCNVA
 (≥10 letters on the Sloan Near Vision Chart at 14 cm) at 12 months from baseline.
- Incidence of secondary surgical intervention (SSI).
- Successful delivery of the IOPCL AMD-MAG as determined at all postoperative scheduled visits starting at 7-14 days post-operative.
 - No capsular tear
 - No visible damage to either the PCIOL or the IOPCL AMD MAG
 - o Uniform leaflet coverage of all IOPCL AMD MAG haptic tabs
- Long-term adherence and positional stability
 - O Gap: Minimal change in uniformity of the gap between consecutive scheduled visits at 1-2 months and later as determined by UBM measurements. Minimal change is defined as +/- 10 microns between visits is established and maintained using UBM imaging.
 - o Tilt:
- Tilt of the PCIOL as determined at all post-operative scheduled visits starting at 30-60 days post-operative. Minimal tilt of the PCIOL confirmed via penlight examination and defined as ≤ 10 degrees between the postoperative tilt of the PCIOL and the pre-operative tilt of the PCIOL.
- Tilt of the IOPCL AMD-MAG as determined at all post-operative scheduled visits starting at 30-60 days post-operative. Minimal tilt of the IOPCL AMD-MAG (using the PCIOL as a reference point) confirmed via penlight examination and defined as ≤ 10 degrees between the post-operative tilt of the. PCIOL and the postoperative tilt of the IOPCL AMD-MAG.
- O Decentration: Decentration as determined at all post-operative scheduled visits starting at 7-14 days post-operative. Centration of the IOPCL AMD-MAG (using the PCIOL as a reference point) confirmed during slit lamp examination and defined as uniform exposed area of the PCIOL outside of the IOPCL AMD-MAG at the vertical and horizontal meridians between ≥ 0.25 mm and ≤ 0.75 mm.
- Counts and percentages for incidence of cumulative and persistent intraoperative and post-operative adverse events
- Counts and percentages for incidence of secondary surgical interventions (e.g., removal
 of interlenticular opacity, repositioning of IOPCL, explant of IOPCL, repositioning of
 PCIOL) (excluding Nd:YAG treatments for PCO).

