15. CLINICAL ASSESSMENTS

All parameters will be recorded for both eyes at baseline (pre-operative). Measurements will be recorded for the study eye at postoperative and post-removal visits. See Appendix 2A schedule of visits (pre- and post-operative visits) and Appendix 2B (post-removal visits). See Appendix 3 for clinical assessment instructions.

Order of Clinical Assessments:

- Mesopic contrast sensitivity testing should be performed prior to the slit lamp examination
 and before any visual acuity testing that requires bright light directed at the subject (i.e., a
 reading lamp shined directly over the subject's shoulder onto the reading card).
- Confirmation of IOPCL location should be performed after the study eye is dilated.

Study sites are expected to implement COVID-19 pandemic safety measures in accordance with their local, state, and CDC health guidelines to ensure the health and well-being of the subjects and study staff who come in contact with the subjects.

Clinical Assessments and Timepoints

- Inclusion/exclusion criteria: Preoperative
- Medical history: Preoperative
- External magnifier usage: Preoperative, 30-60 days, 120-180 days, 330-420 days. Interim
 - Post-removal, 30-60 days, 120-180 days, 330-420 days, Interim
- Demographics: Preoperative
- Patient Informed Consent: Preoperative
- Capsulorhexis Size at the time of PCIOL surgery: Preoperative
- Position of PCIOL Haptics and Planned IOPCL Incision Location: Preoperative
- Axial Length: Preoperative
- Keratometry: Preoperative

- Mesopic and Photopic Pupil size measured by Pupillometer: Preoperative.
- Pseudophakic PCIOL power with make and model number: Preoperative.
- Simulation of expected outcome (3.0D lens over manifest refraction at 30cm and 7.0D lens over manifest refraction, at 14cm and preferred distance): Preoperative.
- Ocular Dominance: Preoperative
- Optical Coherence Tomography: Preoperative, 30-60 days, 120-180 days, 330-420 days.
 Interim
 - Post-removal, 30-60 days, 120-180 days, 330-420 days, Interim
- Capsular Stability: Preoperative, Operative, 7-14 days, 30-60 days, 120-180 days, 330-420 days, Interim
 - Post-removal, 7-14 days, 30-60 days, 120-180 days, 330-420 days, Interim
- Spatial Visualization between the PCIOL and IOPCL Using UBM: 30-60 days, 120-180 days, 330-420 days, Interim.
- Recording of the IOPCL Surgical Procedure: Operative
- IOPCL Location and Confirmation of Incision Location: Operative

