16.3. Postoperative Ocular Adverse Events

Endophthalmitis

- Toxic Anterior Segment Syndrome (TASS)
- Chronic Anterior Uveitis
- Hyphema
- Hypopyon
- Implantable Pseudophakic Contact Lens Dislocation
- Cystoid Macular Edema
 - Clinically Significant Cystoid Macular Edema with reduction in BCDVA of 20/40 or worse at Form 3 (1-2 months post op) or later
- Pupillary Block
- Mechanical Pupillary Block
- Retinal Detachment
 - Rhegmatogenous Retinal Detachment
- Malpositioned/Misaligned Optics (IOPCL not centered over PCIOL and with unequal leaflet coverage of all IOPCL haptic tabs, or IOPCL tilted away from the PCIOL and without anterior leaflet coverage)
 - Early onset: occurring prior to Form 4 visit window (i.e., < 120 days)
 - o Late onset: occurring \ge 120 days
- Unseated IOPCL haptic tabs (One or more haptic tabs not securely attached to the PCIOL)
- Lens Optical Performance
- Mechanical Failure (Tear in haptic tab)
- Vitreous Aspiration for Pupillary Block
- Corneal Stroma Edema
 - o Corneal Edema with BCDVA of 20/40 or worse at Form 3 (1-2M post-op) or later
- Iritis present at 1-month or later
- Macular Edema present at 1-month or later
- Raised IOP requiring treatment
 - o Raised IOP, greater than 10 mmHg above baseline or greater than or equal to 25 mmHg.
- Iris Chafing
- Iris Trauma
- Iris Transillumination Defects

- Pigment Dispersion
- Pseudophacodonesis or Evidence of Zonular Trauma/Dehiscence
- Inter-device opacification or fibrosis between the PCIOL and IOPCL
- Ruptured capsular tissue
- Patient Reported Symptoms described as severe.
- Inability to go down steps, stairs or curbs in dim light or at night due to postoperative vision
- Inability to notice objects in the periphery while walking due to postoperative vision
- Other

Note: Secondary Surgical Intervention(s) (SSI) may be necessary to resolve any of the adverse events identified above. If an SSI is conducted in the trial, the details of the SSI and corresponding reason for SSI will be documented on the SSI CRF.

Examples of Secondary Surgical Interventions

- Irrigation of IOPCL/PCIOL Interface
- IOPCL Exchange
- Reposition of the same Implantable Pseudophakic Contact Lens
- IOPCL Removal
- Iridectomy for Pupillary Block

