# 3.2 Safety Endpoints

• Preservation of Best Corrected Distance Visual Acuity (BCDVA)

The preservation of BCDVA is defined as proportion of eyes (< 5%) that lose two or more lines (≥10 letters) of BCDVA at 12 months from baseline.

• Preservation of Best Corrected Near Visual Acuity (BCNVA)

Proportion of eyes (<5%) that lose two or more lines of BCNVA (≥10 letters on the Sloan Near Vision Chart at 14 cm) at 12 months from baseline.

- Incidence of secondary surgical intervention (SSI)
- Successful Delivery of the IOPCL as determined as all postoperative scheduled visits starting at 7-14 days postoperative.

The successful delivery of the IOPCL is defined as no capsular tear, no visible damage to either the IOL or IOPCL, and uniform leaflet coverage of all IOPCL haptic tabs.

• Long-term Adherence and Positional Stability

The long-term adherence and positional stability is defined as 1) minimal change in uniformity of the gap between consecutive scheduled visits at 1-2 months and later as determined by UBM imaging (where minimal change is defined as +/- 10 microns between visits established and maintained using UBM imaging).

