# 7.5.5 Long-term Adherence and Positional Stability

The analysis of this clinical outcome will be based on the observed data of IOPCL AMD-MAG IOPCL. The number and percent of eyes with established and maintained central spacing as determined by UBM imaging between the IOPCL and IOL will be reported. The number and percent of eyes reporting decentration of the IOPCL or tilt of the PCIOL and/or IOPCL will be reported.

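### The Gap component of the adherence endpoint tests constancy but sets no limit on the gap, so an unattached lens with a stable gap can be counted as a success

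*Protocol*

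**What the plan says.** Protocol section 4 gives the primary objective as "to determine the stability of the IOPCL-AMD-MAG to successfully adhere to a pseudophakic intraocular lens without rotation or slippage". SAP section 2 repeats it.

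Protocol 4.1 places three components under long-term adherence and positional stability: Gap, Tilt and Decentration. The Gap component is "Minimal change in uniformity of the gap between consecutive scheduled visits at 1-2 months and later as determined by UBM measurements", and its tolerance reads "Minimal change is defined as +/- 10 microns between visits is established and maintained using UBM imaging". SAP 3.2 defines the endpoint by the gap alone, as "minimal change in uniformity of the gap between consecutive scheduled visits at 1-2 months and later as determined by UBM imaging". It numbers this item 1 with no item 2, and lists tilt and decentration as separate bullets.

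Protocol 15 schedules the imaging as "Spatial Visualization between the PCIOL and IOPCL Using UBM: 30-60 days, 120-180 days, 330-420 days, Interim". There is no scheduled UBM at surgery, at 1-2 days or at 7-14 days.

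SAP 7.5.5 will report "The number and percent of eyes with established and maintained central spacing as determined by UBM imaging" between the two lenses, and then gives separate counts for decentration and tilt. Protocol 16.3 lists among the postoperative adverse events "Unseated IOPCL haptic tabs (One or more haptic tabs not securely attached to the PCIOL". SAP 7.5.6 tabulates adverse events by visit and over the study.

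**The concern.** The objective concerns a lens that adheres, but the only UBM criterion concerns a gap that does not change. The first reading, at 30-60 days, becomes the reference whatever its size. A lens that had lifted evenly by then, or whose tabs never engaged the PCIOL edge, passes if it then stays where it is.

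Nothing in the SAP links the unseated-tab adverse event to the gap count. One eye could appear in the adverse event table as having an unattached tab and in the SAP 7.5.5 table as having its spacing established and maintained. With so few eyes, one such case materially changes the picture that the study gives of attachment.

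**Working it through.** The documents give no derivation for the 10-micron tolerance and no expected gap, so there is no figure to reproduce. The check applies the rule as written.

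Inputs:
- Tolerance of 10 microns between successive UBM visits (Protocol 4.1, SAP 3.2).
- Three scheduled UBM visits, Forms 3, 4 and 5, hence two comparisons (Protocol 14 and 15).
- Optic diameter 4.5 mm (Protocol 3).
- IOPCL tilt of at most 10 degrees relative to the PCIOL; exposed PCIOL margin of 0.25 to 0.75 mm (Protocol 4.1).
- At most 10 eyes (SAP 6.2).

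**Step 1, the gap rule.** With g3, g4 and g5 the gaps at Forms 3, 4 and 5, an eye passes if |g4 − g3| ≤ 10 and |g5 − g4| ≤ 10. The gap values below are hypothetical.

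| Gaps (microns) | Changes | Result |
|---|---|---|
| 0 / 0 / 0 | 0, 0 | pass |
| 30 / 35 / 38 | +5, +3 | pass |
| 300 / 305 / 308 | +5, +3 | pass |
| 500 / 505 / 500 | +5, −5 | pass |
| 500 / 560 / 480 | +60, −80 | fail |
| 30 / 15 / 14 | −15, −1 | fail |
| 0 / 10 / 20 | +10, +10 | pass |

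Adding the same constant to all three readings never changes the result: 30 / 35 / 38 plus 270 is 300 / 305 / 308. The rule carries no information on the size of the gap. It does fail a loose lens that moves (row 5). It also fails a gap that is closing (row 6), and it passes a net drift of 20 microns because only neighbouring visits are compared (row 7).

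**Step 2, what is measured.** Protocol 4.1 and SAP 3.2 refer to the uniformity of the gap, SAP 7.5.5 to central spacing. If uniformity means the difference in gap across the lens, an even lift adds the same amount everywhere and leaves that difference unchanged. The conclusion is the same on either reading.

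**Step 3, whether the other measures close the hole.**
- *Tilt:* 10 degrees across the optic is 4,500 microns × sin(10°) = 781 microns edge to edge. Conversely, 10 microns edge to edge is arcsin(10 / 4,500) = 0.13 degrees. An evenly lifted lens has zero relative tilt.
- *Decentration:* this is lateral. A lens lifted along the axis can be centred.
- *Leaflet coverage (successful delivery, Protocol 4.1):* this shows that the tabs lie under the capsule, not that the pawl holds the PCIOL edge, which is the locking mechanism described in Protocol 3.
- *Malposition adverse event (Protocol 16.3):* this needs decentration with unequal coverage, or tilt without coverage. An even lift with the tabs covered meets neither.
- *Unseated-tab adverse event (Protocol 16.3):* this does record non-attachment, but no text removes the eye from the SAP 7.5.5 count.

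**Step 4, weight of one eye.** 1/10 = 10 percentage points. SAP 6.5 uses available data without imputation, so missing UBM readings increase it: with 8 eyes, 1/8 = 12.5 points.

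**The case against.** The strongest reply is that the objective concerns the *stability* of adherence, for which a between-visit criterion is a reasonable measure, and that attachment is checked elsewhere. Protocol 12.1.4 has the surgeon confirm that each haptic is seated and holds the PCIOL edge. Lens location is examined from 1-2 days (Protocol 15), and centration and leaflet coverage from 7-14 days (Protocol 4.1). Unseated tabs, dislocation and malposition are all reported as adverse events. The study is descriptive, so a reader of the full report would see an unattached lens.

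Much of this stands, and it rules out several stronger statements that a reader might infer:
- *The whole endpoint has no absolute limit.* The Protocol version has absolute tilt and centration limits.
- *Any lens that never adhered will pass.* It passes only if its gap stays within 10 microns between visits.
- *The primary objective can be declared met on this count.* No rule declares it met, and the Gap component has no success proportion.
- *The gap in microns will not be summarised.* SAP 3.3 lists the UBM assessment as an outcome, and SAP 6.1 gives descriptive statistics for continuous variables. What is missing is an explicit UBM summary in SAP 7.5.7.
- *Early movement is invisible.* Lateral movement before 30 days is observable; axial lift has no scheduled UBM reading then.
- *A gap of 300 microns means detachment.* The documents give no nominal gap, so no value can be labelled that way.

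The reply does not answer the narrower point. The count offered as evidence on adherence cannot itself distinguish an attached lens from a stationary unattached one, and an eye with a recorded unseated tab stays in its numerator.

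**Conclusion.** The concern holds for the Gap component and for the SAP 7.5.5 count built on it. The criterion measures constancy after 30-60 days, sets no limit on the gap and leaves *established* undefined. An unattached lens with a stable gap can be scored as a success, at a cost of at least 10 percentage points per eye. How often this would happen cannot be estimated from the documents.

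The conclusion assumes that the count uses the written rule alone. The clinical methods (Appendix 3) and case report forms (Appendix 8) were not available and may say where the gap is read. Unless they also define an attached gap or exclude eyes with unseated tabs, they would not change the conclusion. This is a correctable flaw in an endpoint definition, not evidence that detachment would go unreported.

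**What to change.** In SAP 3.2 and 7.5.5, and in Protocol 4.1, count an eye as adherent only if it meets the existing 10-micron rule and no unseated haptic tab is recorded at Form 3 or any later visit. Name one measured quantity, central gap or uniformity, in all three places.

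Add to SAP 7.5.7 a summary of the UBM gap in microns at each visit (mean, SD, median, minimum, maximum). Add a per-eye listing that shows the gap beside tilt, decentration and unseated-tab events. The listing would also expose slow net drift.

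If the sponsor has a nominal design gap and tolerance, use them to define *established* for the central gap at Form 3, and fix this before the 4-6 month interim analysis in SAP 6.8. If not, call the endpoint gap stability rather than adherence. The documents give no basis for a numerical limit, and none is proposed here.

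The cost is wording and one listing, using UBM and adverse event data already planned, with no added visit. The downside is that the reported adherence rate can only stay the same or fall, by at least 10 percentage points for each eye reclassified.

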3. INTRODUCTION AND RATIONALE

The IOPCL (intraocular pseudophakic contact lens) AMD-MAG consists of a 4.5 mm diameter concave-convex optic with three opposing haptic straps, or tabs. The central 1.8 mm of the anterior surface of the optic has a power of 10 diopters. The haptic straps are designed to enter and rest within three channels created under the anterior leaflet of the capsular bag. Each channel is created with a Capsule Separator spatula. Each haptic strap or tab has a small pawl, or ridge on the bottom that is used to catch and lock on to the PCIOL optic edge. This pawl aids in both centering the IOPCL AMD -MAG on the PCIOL optic as well as allowing the haptic strap to stay securely seated while contained under the surface tension of the anterior leaflet of the capsular bag. The lens is designed to improve near vision of the AMD subject by providing magnification of 10 diopters in the central 1.8mm zone of the lens optic to improve near vision.

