5.1. Inclusion Criteria

- 1. Subjects aged 55 years or older.
- 2. Subjects who have already had cataract surgery with an Alcon SN60WF, SA60AT or SA60WF monofocal intraocular lens with a lens power between 17.0 diopters and 24.0 diopters clearly evidenced by photographic documentation by one of the following:
 - patient medical record
 - clinic chart with labeling attached
 - surgical record with labeling attached, or
 - patient identification card with make, model and serial number.
- 3. Subjects who have already had cataract surgery at least 6 months from the planned date of the IOPCL surgery.
- 4. Subjects with non-neovascular dry AMD or stable wet AMD meeting the following criteria:
 - No macular fluid retention in the past 12 months
 - No treatment within the past 12 months
 - No change in Amsler Grid test within the past 12 months
 - No subretinal fluid or macular hemorrhage confirmed by optical coherence tomography (OCT) imaging.
 - No fundoscopic changes within the past 12 months (i.e., changes in retinal pigment epithelium).
- 5. Subjects with best corrected distance visual acuity from 20/80 to 20/800.
- 6. Subjects with a preoperative manifest refraction spherical equivalent (MRSE) of +1.0D to -1.0D.
- 7. Subjects with ≤1.0D of corneal cylinder determined by keratometry readings.
- 8. Subjects who are unsatisfied with their current near vision correction provided by either spectacles or external magnifier.
- 9. Subjects who have experienced and failed one or more high-magnification refractive correction alternatives to the IOPCL AMD-MAG.

- 10. Subjects who demonstrate at least 10 letters of near visual acuity improvement with the simulation/tolerance test (using manifest refraction with +7.0D add) compared to conventional near vision testing (using manifest refraction with +3.0D add).
- 11. Subjects with a minimum endothelial cell count of 1800 cells/mm².
- 12. Subjects willing to abstain from pursuing any other surgical vision-correcting procedures for the duration of the study.
- 13. Subjects who are willing and able to complete all required postoperative visits.
- 14. Subjects who are able to comprehend and sign a statement of informed consent.

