12. SURGICAL TECHNIQUE: INSERTION AND REMOVAL INSTRUCTIONS

Video recordings will be created for each subject surgery and provided to the Sponsor for future review and assessment. **Prior to recording the case, please ensure that the video equipment is in full working order**. Video recordings will be shared with the FDA.

Any deviations from the surgical techniques described in the following sections should be captured as protocol deviations.

The Intraocular Pseudophakic Contact Lens (IOPCL) AMD-MAG is designed to improve near vision in the pseudophakic eye with AMD. Using a novel tripod haptic design (see figure 1) placed within 3 channels created under the anterior leaflet of the capsular bag, the optic is designed to self-center, secured over the existing posterior chamber intraocular lens (PCIOL). Each haptic has a ridge that acts as a pawl on the bottom that catches and locks onto the PCIOL optic edge. This pawl aids in both centering the IOPCL on the PCIOL optic as well as securely seat the haptic while contained under the anterior leaflet of the capsular bag. The lens is 4.5mm in diameter with the 3 extending haptics arranged in an isosceles pattern to avoid interference with the haptic/optic junctions of the existing PCIOL. The apex and leading tab are marked R to identify the anterior surface of the lens and prevent inverse implantation and help guide positioning onto the existing PCIOL. When the lens is right-side up the R should be visible and properly oriented when implanting the IOPCL.

Figure 1 - IOPCL AMD-MAG

[figure not shown]

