#### 3.3 Other Clinical Outcomes

- Visual acuity parameters (BCDVA, BCNVA, UCDVA, UCNVA)
- MRSE stability
- Add power
- Slit lamp examination including assessment capsular stability, decentration and tilt
- Gonioscopy
- Reading speed
- Contrast sensitivity (mesopic)
- Applanation intraocular pressure (IOP) using Goldmann

- Dilated fundus examination
- Optical coherence tomography (OCT)
- Spatial visualization between PCIOL and IOPCL using ultrasound biomicroscopy (UBM)
- Specular microscopy
- Visual symptoms (VFQ-25)
- External magnifier usage

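### The 0.25 to 0.75 mm centration window mixes size with displacement, and only counts are planned, so a shift inside the window would not be reported in millimetres

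*Protocol*

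**What the plan says.** The primary objective in Protocol 4 is for the IOPCL "to successfully adhere to a pseudophakic intraocular lens without rotation or slippage". Among the position endpoints in Protocol 4.1, centration is checked at the slit lamp from the 7-14 day visit onward, with the PCIOL as reference. It requires a uniform "exposed area of the PCIOL outside of the IOPCL AMD-MAG at the vertical and horizontal meridians between ≥ 0.25 mm and ≤ 0.75 mm". SAP 3.2 repeats this definition without further detail.

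Two sections give the device size: Protocol 3 says it "consists of a 4.5 mm diameter concave-convex optic with three opposing haptic straps, or tabs", and Protocol 12 says "The lens is 4.5mm in diameter with the 3 extending haptics arranged in an isosceles pattern". Protocol 5.1 identifies the underlying lens by model and power only: "cataract surgery with an Alcon SN60WF, SA60AT or SA60WF monofocal intraocular lens with a lens power between 17.0 diopters and 24.0 diopters". Exclusion criterion 7 in Protocol 5.2 keeps the capsulorhexis, at the time of PCIOL surgery, between 5 and 6.0 mm.

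For analysis, SAP 7.5.5 plans the number and percentage of eyes with decentration. SAP 3.3 also lists "Slit lamp examination including assessment capsular stability, decentration and tilt", and SAP 7.5.7.5 summarises slit lamp findings as numbers and percentages by visit.

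**The concern.** A rim width depends on two things: how large the outer boundary is relative to the 4.5 mm optic, and how far the optic has moved. A fixed window on the rim tests both at once. The same displacement can therefore pass in one eye and fail in another because of size alone, if the boundary differs between eyes.

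The primary objective is about movement, and decentration is the only listed position endpoint with a numeric lateral limit. Gap is an axial measure and tilt an angular one. Leaflet coverage, unseated tabs, dislocation and repositioning also bear on position but carry no lateral distance. The malposition event joins two findings, "IOPCL not centered over PCIOL and with unequal leaflet coverage of all IOPCL haptic tabs", again without a distance. Protocol 4.1 defines gap as a change between visits and tilt as a difference from a reference tilt. Decentration is a pass or fail at each visit, so slippage inside the window would not appear in the planned tables.

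**Working it through.** **Inputs.** IOPCL optic diameter 4.5 mm (Protocol 3 and 12). Window 0.25 to 0.75 mm (Protocol 4.1, SAP 3.2). Capsulorhexis 5 to 6.0 mm (Protocol 5.2, criterion 7). The PCIOL optic diameter is not stated, so the outer diameter B is an assumption shown as a range. The limits are read as applying to each side.

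**Where the window may come from.** The plan gives no derivation. A centred optic leaves a rim of g = (B − 4.5)/2. The capsulorhexis limits reproduce the window exactly: (5.0 − 4.5)/2 = 0.25 mm and (6.0 − 4.5)/2 = 0.75 mm. This suggests, but does not show, that the capsular opening is the intended boundary.

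**Tolerated shift.** A shift s along one meridian gives opposing rims g − s and g + s. Both must lie in 0.25 to 0.75 mm, so the largest passing s is min(g − 0.25, 0.75 − g) = 0.25 − |g − 0.50|.

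| Assumed B (mm) | Centred rim g (mm) | Largest passing shift (mm) |
|---|---|---|
| 4.9 | 0.20 | no position passes |
| 5.0 | 0.25 | 0 |
| 5.25 | 0.375 | 0.125 |
| 5.5 | 0.50 | 0.25 |
| 5.75 | 0.625 | 0.125 |
| 6.0 | 0.75 | 0 |
| 6.1 | 0.80 | no position passes |

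**Same shift, different result.** A 0.15 mm shift leaves rims of 0.35/0.65 mm at B = 5.5 (pass), 0.225/0.525 at 5.25 (fail) and 0.475/0.775 at 5.75 (fail). In general a shift s passes only for B from 5.0 + 2s to 6.0 − 2s; for 0.15 mm that is 5.3 to 5.7 mm.

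**Movement between visits.** At B = 5.5, rims of 0.25/0.75 mm at one visit and 0.75/0.25 mm at the next both meet the limits. The lens has moved 0.25 + 0.25 = 0.5 mm. The other meridian passes as well: with R = 2.75, r = 2.25 and a 0.25 mm shift, its rims are 2.75 − √(2.25² − 0.25²) = 0.514 mm.

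**Oblique shifts.** For a diagonal shift with components a and a at B = 5.5, the wider rim reaches its limit when 2.75 + a − √(2.25² − a²) = 0.75. This gives 2a² + 4a − 1.0625 = 0, so a = 0.237 mm and the total displacement is 0.237 × √2 = 0.336 mm.

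**If 'uniform' means exactly equal rims.** No shift passes at any B, and the window then checks only that B is 5.0 to 6.0 mm. No tolerance for 'uniform' is given in the supplied text.

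**A measure free of B.** For displacement (x, y) and circular boundaries, the horizontal rims are R − x − √(r² − y²) and R + x − √(r² − y²). Half their difference is x, whatever R and y are. The vertical pair gives y in the same way.

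**What a count can show.** With 0 of 10 eyes decentred, the exact two-sided 95% upper limit is 1 − 0.025^(1/10) = 30.8%.

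**The case against.** The strongest reply is that the window is coherent and that its harm is unproven. If the boundary is the capsular opening, the limits match the eligible range exactly. If it is the PCIOL edge, its diameter is a fixed attribute of three named models that the sponsor can look up. Near 5.5 mm the rule does its job. Protocol 15 also schedules IOPCL location after dilation at every postoperative visit. The measurement instructions and case report forms (Appendices 3 and 8) were not supplied and may define 'uniform' or record distances. SAP 6.1 has a general rule for summarising continuous variables. No hypothesis test, success threshold or stopping rule uses decentration.

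Most of this stands, and it limits the size of the point. It does not remove it. On the capsular-opening reading, size still enters the position rule and can differ between eligible eyes. That reading is also unsettled, because the text names the PCIOL as reference. SAP 6.1 names no decentration distance.

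Three stronger inferences are tempting but not supported:

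- A reader might conclude that a centred lens cannot pass. That needs a B at or beyond the ends of the 5.0 to 6.0 mm range, and the documents do not give B.
- A reader might sum the two sides, so that the window would not limit shift along a meridian at all. The protocol's revision summary describes the upper limit as a maximum distance, which fits a single rim better than a sum.
- A reader might take the 0.5 mm movement as certain to be missed. An examiner could call rims of 0.25 and 0.75 mm non-uniform and fail the eye.

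**Conclusion.** The point holds as a modest measurement weakness. Read per side, the tolerated shift along one meridian runs from 0 to 0.25 mm over B = 5.0 to 6.0 mm, and nothing passes outside that range. How much this matters depends on B, which the supplied text does not fix. Regardless of B, the planned summaries give no displacement and no between-visit change in millimetres, although slippage is the primary objective.

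The conclusion assumes per-side limits, near-circular boundaries, and that the unseen appendices do not already supply the missing measurement. The 0.5 mm movement further assumes B = 5.5 mm and that 'uniform' adds no tighter limit. In a descriptive study of at most 10 eyes this changes no formal decision. It changes how much each eye can tell the sponsor about stability.

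**What to change.** In Protocol 4.1 and SAP 3.2 and 7.5.5:

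- Record the two opposing rims at the vertical and the horizontal meridian at each scheduled visit from 7-14 days. Measure to the PCIOL edge where it is visible in the dilated eye; otherwise note which boundary was used.
- Derive signed displacement per meridian as half the difference of the opposing rims, with a fixed sign convention. This is exact for circular boundaries and is relative to the boundary used. If the boundary is the capsular opening, it gives offset from that opening, which need not share a centre with the PCIOL.
- List each eye, and summarise by visit the size of displacement and its change between visits in millimetres, beside the existing number and percentage. Flag any change computed across two different boundaries.
- State which boundary the window refers to, that the limits apply per side (if so intended), and what 'uniform' means. Reconcile 0.25 to 0.75 mm with the 4.5 mm optic and the diameter of that boundary. No limit is proposed here.

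The cost is some wording, one derived variable per meridian and possibly four rim fields on the case report form. A per-side rule already needs these readings, and Appendices 3 and 8 may already provide for them.
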